We aim to have a sample that would yield .80 power in longitudinal analysis with generalized estimating equations model (a type of generalized linear mixed models) to find a standardized detectable difference from .4 to .5 between intervention and usual care, assuming alpha = .05, two-tailed. We assume that the correlation between repeated measures will be .60. The outcome of treatments will be measured at two points in time (3-month and 9-month) for each individual. The sample size for our primary hypothesis (difference in slopes by treatments) is based on Diggle, Liang, and Zeger, who developed a formula to calculate sample size for longitudinal studies with repeated measures to estimate the difference between slopes (or rate of change in CAPS as in this case) of two groups (m = size per arm):

$$M = 2(Z_{\alpha} + Z_{\beta})^{2} \sigma^{2} (1 - \rho) / (nS_{x}^{2} d^{2})$$

where $S_x^2 = \sum_j (x_j - \bar{x})^2 / d$, the within-subject variance of the x_j ; type I error α = 0.05, power β = 0.8 and the smallest meaningful difference d = $\beta_{1B} - \beta_{1A}$ and σ^2 = $Var(\epsilon_{ij})$ measures the unexplained variability in the response, $Corr(Y_{ij}, Y_{ik}) = \rho$ for all $j \neq k$, and n is the number of repeated measures per person.

Using this formula and based on these assumptions, we estimated the sample size needed. Table 2 shows how required total enrollment (both groups) would vary for a range of expected effects and if the true effect is larger or smaller than expected for a range of possible missing data scenarios.

Table 2. Enrollment Number N (total of two groups) as a function of effect size and rates of missing endpoints due to drop out and loss to follow-up

	Loss to Measurement						
actual effect size	10%	15%	20%				
.40	160	169	180				
.45	126	134	142				
.50	102	108	115				

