Therapists will be selected by the site principal investigator. We will not screen out therapists for this study based on any pre-existing criteria, experiences, or credentials. Several studies now demonstrate the feasibility of training community clinicians in manualized, cognitive behavioral treatments for trauma. Rape crisis counselors, community mental health clinicians, and school-based counselors have been shown to be able to learn specific cognitive behavioral interventions and to provide them with good outcome. Each site will work with the PI to identify therapists who are interested in learning CBT for PTSD and in participating in research. Each site will agree to commit 2 staff to serve as research therapists, even though only one is needed. In this way we can respond to any attrition of therapists without losing time.

All therapists will attend a two-day training in CBT for PTSD offered by [name] (PI) and [name] (Co-I). This training, initially developed for the disaster treatment context, has been modified to include a specific module summarizing the research with co-occurring PTSD and substance use disorders and includes PTSD/SUD case examples. The training in CBT for PTSD includes a combination of modalities such as lecture, practice exercises, expert demonstration (including live and video demonstrations), and role plays. The

training begins by providing therapists with a solid rationale for the intervention. In presenting the rationale, trainers review empirical research on other PTSD/SUD treatments, such as Seeking Safety, and share the philosophy behind the development of this model. The goal is to establish the credibility of the treatment with the therapists. Next, therapists are taken step-by-step through each session of the intervention. Session goals are emphasized and suggestions for meeting those goals are provided. Therapists are shown how to use the manual during the session, how to integrate handouts into the teaching of the intervention, and how to address specific problems that may arise.

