In advance, therapists will be provided with the adherence and competence measures for CBT for PTSD (Adherence and Competence [ACI] Index) so they know how their audio recordings will be evaluated. In addition, therapists will keep a session-by-session "Therapist Session Tracking Form".

All sessions will be audio recorded. Digital recordings will be uploaded to the secure server at Research Services at the White River Junction VA. [name], one of the original developers of CBT for PTSD, will rate a random sample of 15% of all recorded sessions for each therapist by using the ACI and adherence and competence measures. From our earlier studies, we expect the therapists to be competent and adherent in delivering CBT.

E. Assessments and Data Management

The site coordinator will complete the screening assessment and the assessor will complete the eligibility, baseline, and follow-up assessments. Pilot testing indicates the baseline assessment will take 3.4 hours to administer and the follow-up interviews will take 2.1 hours to administer. Assessments will be done in person whenever possible. Assessments will occur by phone if necessary, so that data is not lost. The same assessors will be used for both methods.

All assessment instruments are described in detail below and summarized in Table 4.

1. Screening

The PC-PTSD⁷⁷ is a brief 4-item screen for PTSD. The PC-PTSD was developed with VA primary care patients, where the instrument detected PTSD diagnoses more accurately than did clinician diagnosis. In an

SUD population the PC-PTSD has a sensitivity of .90, and a specificity of .77. This screen has been adopted for use in all returning Iraq/Afghanistan Veterans and as a performance measure for primary care. The screen will be used to identify patients in need of full PTSD assessment to determine eligibility for the treatment trial prior to randomization.

2. Eligibility

Sociodemographics. Brief assessment of patient's social and demographic characteristics such as age, gender, marital status, and level of education. Measure includes questions on periods of service and disability status.

Life Events Checklist: The Life Events Checklist is used with the Clinician Administered PTSD Scale as a measure of trauma exposure. To be eligible for the study, patients need to endorse at least one Criterion A traumatic event. The Checklist will also provide descriptive information about the patients in the study.

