The unit of analysis is the participant. All analyses will be initially conducted according to intention-to-treat, i.e., participants' data will be analyzed according to their assigned group regardless of their actual exposure to treatment. Prior to analysis, we will carefully examine descriptive statistics and the distributional form of all variables. We will use appropriate transformations, recode or categorize skewed and abnormally distributed data, and use appropriate methods for outliers and missing data so that we do not violate assumptions of our statistical procedures. Imputation techniques for missing data, such as linear interpolation and multiple imputations will be examined to determine their effect on the results. It is recognized, however, that the best approach to missing data is to make all effort to minimize it, since imputation is difficult when the missing data are non-ignorable or not missing at random. Our aim is to use careful examination and planned procedures so that we minimize the number of statistical tests, thereby reducing the possibility of inferential errors. Therefore, for tests of hypotheses 1 and 2, we will not use a downward adjustment of alphas (from .05) as the analysis and hypotheses have been planned and stated a priori.

1. The effects of CBT on patient outcomes

Hypothesis 1 (primary): Patients exposed to CBT will have greater improvements in PTSD symptom severity relative to patients who receive TAU as measured by the CAPS total score, and secondarily by the PCL, from baseline to post-treatment and 6 month follow-up.

Hypothesis 2 (secondary): Patients receiving the CBT will have greater reductions in substance use severity (drugs and/or alcohol) relative to patients who receive TAU as measured by the ASI drug and alcohol severity composite scores, and secondarily by the TLFB, from baseline to post-treatment and 6 month follow-up.

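### The plan makes no allowance for therapist clustering in the CBT arm; at an assumed ICC of 0.01 to 0.05, true alpha is about 6% to 12% and power about 61% to 78%

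*Combined protocol and SAP*

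**What the plan says.** **Delivery.** CBT is individual therapy (IV.C.1). On staffing, IV.D says: "Each site will agree to commit 2 staff to serve as research therapists, even though only one is needed". The site-personnel description before the reference list likewise has one 0.2 FTEE therapist giving CBT and a second trained as cover. Three sites are named (IV.B.4 and IV.B.5). IV.C says that CBT therapists give no TAU services to study patients.

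**Sizing.** IV.B.6 sets the target: "We aim to have a sample that would yield .80 power", for "a standardized detectable difference from .4 to .5 between intervention and usual care", "assuming alpha = .05, two-tailed". The only correlation allowed for is within patient: "We assume that the correlation between repeated measures will be .60".

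**Analysis.** IV.G states "The unit of analysis is the participant". The model has fixed effects for baseline PTSD severity, intervention, time and treatment by time, with a patient-level random intercept and slope. Site is a possible covariate. Site-by-treatment interaction is to be examined, with none expected. Therapist does not appear in IV.B.6 or IV.G as a fixed effect, random effect, cluster or sensitivity analysis.

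**The concern.** Patients treated by the same therapist share whatever that therapist does better or worse than others. Here the sharing occurs in one arm only, because TAU study patients never see these therapists. In the team's earlier pilot trial (III.B), each therapist delivered both treatments, so therapist differences fell on both arms. This design does not have that protection.

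If therapists differ in their results, a model that treats CBT patients as independent gives a standard error for the CBT-TAU contrast that is too small for any conclusion reaching past these few therapists. The plan does look past them: the Specific Aims speak of improving treatment for Veterans with substance use disorders and PTSD generally. At stake are the stated error rate and interval for Hypothesis 1, and the 80% power claimed in Table 2.

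**Working it through.** **Inputs from the documents.** Two-sided alpha 0.05; power 0.80; d = 0.40; within-patient correlation 0.60; 80 patients per arm; 10% loss, so 80 × 0.9 = 72 evaluable per arm. Three therapists give 72/3 = 24 CBT patients each; six give 72/6 = 12.

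**Assumption.** Therapist ICC on the analysed scale of 0.01, 0.02 and 0.05. The documents give no value.

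**Step 1: reproduce Table 2.** The time-averaged repeated-measures formula, m per arm = 2(z₀.₉₇₅ + z₀.₈₀)²[1 + (n − 1)ρ]/(n d²), with n = 3 and ρ = 0.6, gives m = 71.95 at d = 0.40. Total enrollment is 2m/(1 − loss):

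| d | 10% loss | 15% loss | 20% loss |
|---|---|---|---|
| 0.40 | 159.9 | 169.3 | 179.9 |
| 0.45 | 126.3 | 133.8 | 142.1 |
| 0.50 | 102.3 | 108.3 | 115.1 |

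All nine cells match Table 2, with no therapist design effect. (The printed slope formula with two measurements, times coded 0 and 1, gives 174/185/196 at d = 0.40. That mismatch is a separate matter.)

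**Step 2: add clustering in the CBT arm only.** With k patients per therapist, the CBT mean's variance is multiplied by 1 + (k − 1)ICC and the TAU mean's is unchanged. The contrast variance is multiplied by

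R = 1 + (k − 1) × ICC/2.

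- True SE / model SE = √R.
- Real alpha of the unadjusted test = 2[1 − Φ(1.96/√R)].
- Power with a corrected SE = Φ(d/(SE√R) − 1.96), where SE = √(2 × 0.7333/72) = 0.1427 and 0.7333 = 2.2/3. At R = 1 this is Φ(2.803 − 1.96) = 80.0%.

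Example, three therapists, ICC 0.05: R = 1 + 23 × 0.05/2 = 1.575 and √R = 1.255. Alpha = 2[1 − Φ(1.562)] = 11.8%. Power = Φ(2.803/1.255 − 1.96) = Φ(0.273) = 60.8%.

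| Therapists | ICC | R | SE ratio | Real alpha | Power, d = 0.40 |
|---|---|---|---|---|---|
| any | 0 | 1.000 | 1.000 | 5.0% | 80.0% |
| 3 | 0.01 | 1.115 | 1.056 | 6.3% | 75.6% |
| 3 | 0.02 | 1.230 | 1.109 | 7.7% | 71.5% |
| 3 | 0.05 | 1.575 | 1.255 | 11.8% | 60.8% |
| 6 | 0.01 | 1.055 | 1.027 | 5.6% | 77.9% |
| 6 | 0.02 | 1.110 | 1.054 | 6.3% | 75.8% |
| 6 | 0.05 | 1.275 | 1.129 | 8.3% | 69.9% |

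The power figures use a normal critical value and are optimistic with so few clusters.

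**Step 3: simulation.** A single endpoint with site fixed effects (three sites, 24 evaluable per arm per site, average effect zero) gives type I error of about 6.4%, 7.8% and 12.1% with three therapists. With six it gives about 5.6–5.8%, 6.3–6.4% and 8.3–8.4%, and at ICC 0 it gives 5.0%. A treatment-by-time contrast over three visits gives 6.3% to 11.5% with three therapists and 5.6% to 8.2% with six, so the result does not depend on the single-endpoint simplification.

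**Step 4: would the planned site check catch it?** With one therapist per site, therapist variation appears as site-by-treatment interaction. The per-site contrast variance is multiplied by [(2 − ICC)/24 + ICC]/[(2 − ICC)/24], that is 1.615 at ICC 0.05 and 1.242 at 0.02. A 2-df chi-square test at 5% (critical value 5.991) then rejects with probability exp(−2.996/1.615) = 16% and exp(−2.996/1.242) = 9%. A non-significant result would say little.

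**The case against.** A reader might infer that the primary standard error is simply wrong and that the 5% level is not held. The documents do not support that.

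- **The ICC is unknown.** At zero the unadjusted test is exact. IV.D also describes steps that should keep therapist differences small: a manual, two-day training, a closely supervised first case kept out of the research, no study cases until delivery is judged acceptable, group supervision every other week, and rating of 15% of each therapist's sessions. These do not show that the ICC is zero, but they are a reason not to presume a large one.
- **The null matters.** CBT is added to TAU. If it does nothing for anyone, therapists cannot differ in effect and randomisation of patients holds the 5% level. The inflated rates require some therapists to help and others to harm, averaging zero. Overstated precision and power are therefore the more natural worry.
- **Inference may be conditional.** Treating a handful of therapists or sites as fixed is defensible. This stands, but the plan does not say that it does so.
- **Site already covers therapist.** A reader might infer that therapist is confounded with site and cannot be addressed. TAU patients identify the site effect, so therapist overlaps only with site by treatment. That planned check, and the site-specific plots, would show some therapist variation. They do not correct the primary standard error, and the check is weak (Step 4).
- **A therapist random effect is nearly uninformative with three therapists.** This stands. With about 2 degrees of freedom the critical value is about 4.3, which is why the fix does not rest on fitting one.
- **Six is not the planned number.** The second therapist is cover. Recruitment over several years may bring replacements, so the final count is unknown and three to six is a working range.

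**Conclusion.** The omission is established: few therapists, nested in one arm, with no allowance in the model or in Table 2. The direction is also clear, since any positive ICC makes the unadjusted standard error too small for inference beyond these therapists. The size is conditional. It rests on an assumed ICC of 0.01 to 0.05, equal caseloads and three to six therapists. Within that range alpha departs little from 5% at the low end and more than doubles at the high end, and the power loss is about 2 to 19 percentage points. The documents do not show that the trial's error rate is in fact inflated. They show that the plan neither allows for the possibility nor states the condition under which its p-value is valid. This should be corrected, but it does not overturn the primary analysis.

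**What to change.** Keep the primary model and make these changes.

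1. **IV.G, sensitivity analysis of Hypothesis 1.** Recompute the confidence interval and p-value with the CBT-arm variance inflated for therapist ICCs of 0.01, 0.02 and 0.05, using actual caseloads. For unequal caseloads k_j the factor is 1 + ICC × (Σk_j²/Σk_j − 1).
2. **IV.G, interpretation.** State that the main p-value is conditional on the participating therapists, and report CBT-arm results by therapist.
3. **IV.G, partially nested model.** Fit it (therapist random effect in the CBT arm only, site fixed, Kenward-Roger degrees of freedom) only if about six or more therapists treat patients.
4. **Table 2.** State that it assumes a therapist ICC of zero, and give the power range of about 61% to 78% at d = 0.40 for ICCs of 0.01 to 0.05 with three to six therapists.
5. **Data set.** Carry the treating therapist's ID into the analysis file. Therapists keep session tracking forms (IV.D), so it should be recoverable, but Table 4 lists no such variable.

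The cost is SAP wording, one derived variable and a short extra analysis, with no new patients or assessments. The price is a wider sensitivity interval and a less favourable power statement.

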Several steps will be taken in preparation for performing the primary analyses. We will evaluate the effectiveness of randomization by comparing CBT and TAU groups on demographics, baseline measures of key outcomes, and other important covariates such as psychotropic medication usage. Next we will perform simple end-point analyses of post-treatment and 6-month outcomes using t-tests (chi-square test for retention proportion) and use multiple linear and logistic regression models to examine predictors of outcome. Demographic variables, baseline severity, and medical and psychiatric comorbidities will be considered as possible covariates. Only covariates that significantly reduce variance will be added to the model.

Because the groups are randomized to be equivalent at baseline, the t-tests and end-point linear regression or logistic regression analyses are valid methods of comparison; however, patients who fail to provide any outcome data (at post-treatment and 6-months) measurement will naturally get excluded from the analyses, and this may introduce bias in the estimates. Furthermore, end-point analyses do not take into account the longitudinal nature of the data, time-varying covariates, or correlations among repeated observations.

For our main analysis, we will perform both cross-sectional and longitudinal analyses using Generalized Linear Mixed Model (SAS PROC MIXED) for continuous outcomes (for example, primary hypothesis) and PROC GLIMMIX for binary outcomes. We will model changes over time at population level. We will examine the

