change in groups over time, i.e., change in treatment slopes over time, and the change in the difference between the slopes over time. We will fit a model that includes the fixed effects of PTSD severity at baseline, intervention, time, and the treatment by time interaction. We further plan to model changes over time at person-specific level by adding a random intercept and random slope to model the heterogeneity between individuals. We expect no significant site main effects or site by treatment interactions, but this will be examined. Although estimating the covariance structures is not a goal of the analyses, we will examine the model fit using different covariance structures as appropriate covariance structure is necessary for valid inferences about fixed effects. Once again, only those covariates that significantly reduce error variance will be added to the model. Demographic variables, baseline scores, baseline symptom severity, and site will be considered as possible covariates. We will plot predicted means for the groups over time, and for each site, along with confidence intervals.

Some simple parametric (e.g. linear or quadratic) curves will be used to describe the changes over time of the mean response. The fitting of parsimonious models for the mean response will result in statistical tests of covariate effect (e.g. treatment by time interactions) that have greater power than, for example, in analysis of response profiles.⁹⁵

If the mean response changes in an approximately linear fashion over the duration of the study, we will adopt the following linear trend model

Hypothesis 1 and 2:
$$E(Y_{ij}) = \beta_1 + \beta_2 Time_{ij} + \beta_3 Group_i + \beta_4 Time_{ij} *Group_i$$

Where $Group_i = 1$ if the i^{th} individual was assigned to the CBT treatment, and $Group_i = 0$ otherwise; and $Time_{ij}$ denotes the measurement time for the j^{th} measurement on the i^{th} individual.

Our primary interest concerns a comparison of the changes in the mean response over time, which is a comparison of the slopes. The slope, or the rate of change in the mean response per unit change in time, is β_2 in the control group, and ($\beta_2 + \beta_4$) in the treatment group. Thus, if β_4 is not significantly different from 0, then the two groups do not differ in terms of changes in their mean response over time.

Assuming that the changes in the mean response can be approximated by quadratic trends, the following model can be adopted:

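### Two of the three randomisation strata, site and substance type, have no assured place in the analysis models; the cost is small and falls mainly on the single-time-point analyses

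*Combined protocol and SAP*

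**What the plan says.** **Randomisation (section IV.F).** Permuted blocks of 2, 4 and 6 are stratified by substance type (two levels), severe PTSD (two levels, no cut-off given) and site. Site is given two levels there. Sections IV.A.1, IV.B.4 and IV.B.5 describe three sites, the third added in August 2013.

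**Longitudinal model (section IV.G.1).** "We will fit a model that includes the fixed effects of PTSD severity at baseline, intervention, time, and the treatment by time interaction". A few lines later severity is a candidate again: "Demographic variables, baseline scores, baseline symptom severity, and site will be considered as possible covariates", subject to the rule that "only those covariates that significantly reduce error variance will be added to the model". The linear and quadratic equations printed for Hypotheses 1 and 2 contain neither severity nor any other covariate. The target is stated as: "Our primary interest concerns a comparison of the changes in the mean response over time, which is a comparison of the slopes".

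**Single-time-point analyses (section IV.G.1).** The end-point regressions come first, as preparation. Their candidates are: "Demographic variables, baseline severity, and medical and psychiatric comorbidities will be considered as possible covariates", and again "Only covariates that significantly reduce variance will be added to the model". Single-time-point work also appears within the main analysis: "For our main analysis, we will perform both cross-sectional and longitudinal analyses".

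**Retention (section IV.G.2).** The example regression for Hypothesis 3 has group, baseline CAPS, age and sex.

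Substance type is named in none of these lists or equations.

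**The concern.** Stratified allocation forces the arms to be alike on the stratification factors. If a factor predicts the outcome and is left out of the model, its contribution stays in the residual variance although the design has already removed it from the sampling error of the treatment difference. The reported standard error is then too large: the test rejects too seldom under the null and has less power than it could.

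The plan gives reason to expect some prognostic value. The pilot account in section III attributes the pattern of drinking and drug results to which substance each arm's patients used, and the Hypothesis 2 outcomes are the ASI alcohol and drug composites. The three programmes in section IV.C.2 also differ in length, intensity and setting.

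Separately, a reader cannot tell from these documents how patients at the third site were stratified, or where the line for severe PTSD was drawn.

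**Working it through.** **1. The plan's sample size.** The 160 in Table 2 (section IV.B.6: d = 0.40, rho = 0.60, 10% loss, two-sided .05, 80% power) reproduces as a time-averaged difference over three measures:

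- per arm, 2 × (1.960 + 0.842)² × [(1 + 2 × 0.60)/3] / 0.40² = 71.9
- total, 2 × 71.9 / 0.90 = 159.9

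No stratum enters this formula, so nothing below changes N. That the printed formula is for slopes is a separate matter.

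**2. Strata.** As written, 2 × 2 × 2 = 8; with three sites, 2 × 2 × 3 = 12.

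**3. Single-time-point analysis.** Simulation, 40,000 trials per setting:

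- From the documents: 160 randomised in blocks of 2/4/6; 10% lost, leaving 144; correlation .60 between baseline and outcome; alcohol-only share 24/86, from the diagnostic percentages in section IV.B.3.
- Assumed: three equal sites; severity split at the median; loss at random; site and substance type together explaining 0, 5 or 10% of the variance left after baseline, split equally between them; treatment effect at noncentrality 2.80.
- Every model contains group and baseline CAPS.

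| Model | Alpha at 0/5/10% | Power at 0/5/10% |
|---|---|---|
| Neither factor | .051 / .045 / .040 | .793 / .801 / .805 |
| Site kept if p < .05, substance type never | .051 / .047 / .044 | .793 / .806 / .817 |
| Both fixed | .051 / .049 / .049 | .791 / .814 / .834 |

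Monte Carlo error is about .001 for alpha and .002 for power. The rule keeps site in 5/37/67% of trials. Its power cost against fixing both is .814 − .806 = 0.8 points at 5%, and 1.6 points at 10% (.834 and .817 before rounding). With neither factor, as in the end-point candidate list, the cost is 1.3 and 2.9 points. With both fixed, the standard error is 1.4% and 2.8% smaller than under the rule. If the factors explain nothing, fixing both costs about 0.3 points.

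Large-sample check with neither factor: alpha = 2 × [1 − Φ(1.96/√(1 − R²))] = .044 at 5% and .039 at 10%, in line with the simulation.

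**4. Slope contrast, factor effects constant over time.** A patient's fitted slope is Σ wⱼyⱼ with wⱼ = (xⱼ − x̄)/SS. Since Σ wⱼ = 0, an effect equal at every visit drops out when data are complete. Simulation with dropout (visits at 0, 4 and 10 months as in section IV.A.1; 1,500 trials per setting) agrees: power .80 with and without the factors at both 5% and 10%, standard error ratio .9995 and .9989.

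**5. Slope contrast, factor alters the course.** For visits 0, 4, 10: x̄ = 4.667 and SS = 50.67. With unit outcome variance the error variance of a slope is (1 − .60)/50.67 = .00789. A factor effect f adds c² × Var(f):

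- effect present only after baseline: c = (−0.667 + 5.333)/50.67 = .0921
- effect growing linearly to f at month 10: c = 1/10 = .100

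Let r = √[.00789/(.00789 + c² Var(f))] be the ratio of the standard error with factor-by-time terms to that without. Power without them is Φ(2.80 − 1.96/r), against Φ(0.84) = .800 with them.

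| Var(f) | Standard error smaller by | Power without the terms |
|---|---|---|
| 5% of variance left after baseline (.05 × .64) | 1.7–2.0% | .790–.788 |
| 10% of variance left after baseline (.10 × .64) | 3.3–3.8% | .780–.777 |
| 5% of total variance | 2.6–3.0% | .785–.782 |
| 10% of total variance | 5.0–5.8% | .770–.764 |

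Alpha without the terms, 2 × [1 − Φ(1.96/r)], is below .05 throughout. Main effects alone do not recover this loss, because step 4 applies to them too.

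**The case against.** **The primary test is not where the loss falls.** A reader might infer that Hypotheses 1 and 2 lose power as a matter of course, since the main analysis includes cross-sectional work. The documents do not support that. Section IV.G.1 gives no model for the cross-sectional part, attaches the label of Hypotheses 1 and 2 to the slope model, and describes the same hypotheses as a change in the mean difference. Constant factor effects cancel there. This stands and limits the point.

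**Selection from outcome data.** A reader might also infer inflated type I error, because alpha is left unadjusted on the ground that "the analysis and hypotheses have been planned and stated a priori", while the covariates depend on the data. But the core terms, candidates and rule are written in advance, and simulated alpha under the rule is .047 and .044 at 5% and 10%. No inflation is shown.

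**Substance type may enter by proxy.** The candidate baseline scores could include the ASI composites, and psychiatric comorbidities could admit a substance diagnosis. Either might carry part of the signal, so the figures above may overstate the loss. Neither names the stratum or ensures that it enters. Site is at least examined for main effects and interaction with treatment.

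**Retention.** The Hypothesis 3 equation is an example, not an exclusive list, and its loss cannot be sized because the number of IOP patients is not given.

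**Randomisation details.** Section IV.H.2 mentions an operations manual, which may record the severity cut-off and the handling of the third site. That would answer the documentation gap but not the conflict in site counts.

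**Conclusion.** The point holds as a minor one. Severity is the only stratification factor fixed in the longitudinal model, and the text is inconsistent even there. Site enters only if significant, and substance type is never named.

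In single-time-point analyses the selection rule costs about 1 to 2 points of power at assumed shares of 5–10%, and up to 2.9 if neither factor enters; the error is on the conservative side. The slope or change contrast loses nothing material if factor effects are constant over time, and about 1 to 4 points if a factor alters the course with shares in that range. There is no evidence of bias or of excess false positives.

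All variance shares are assumptions, as are equal sites and the median severity split. With no prognostic value there is no loss. The conflict between two and three sites is a matter of record and does not depend on any of this.

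**What to change.** - Exempt the stratification factors from the significance rule.
- In the Hypothesis 1 and 2 models and the end-point regressions, always include site, substance type and either baseline CAPS or the severity stratum (one of them; state the cut-off if the stratum is used). Print these terms in the equations.
- In the longitudinal model, also pre-specify site-by-time and substance-type-by-time terms, since main effects alone do not help the slope contrast.
- For Hypothesis 3, add substance type and site, with site limited to the programmes that contribute IOP patients; keep baseline CAPS.
- Reconcile the two sites of section IV.F with the three-site design, and document how third-site patients were stratified.

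Cost: the longitudinal model gains 3 degrees of freedom for main effects (substance type 1, site 2) and 3 more for the linear time interactions (another 3 if the quadratic model is used). The end-point regressions gain 4, because severity is only a candidate there. About 144 patients carry this easily; in the single-time-point analysis the price is about 0.3 power points if the factors explain nothing. Sample size, visits and staffing do not change.
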